6.2.1 Primary efficacy endpoint evaluated in subgroups

Additional analyses of the primary efficacy endpoint will include a Cox proportional hazards regression model to examine selected variables. The analyses will be based on the mITT analysis set. The following baseline covariates will be explored to assess the impact on the vaccine efficacy:

- trial site
- country
- BMI
- age-group
- sex at baseline
- smoking status
- anemia
- diabetes mellitus
- other significant comorbidity at baseline.

See section 4.3 for definition of categories.

Furthermore, the effect of the following will be analysed:

- use of steroids and anti-inflammatory drugs during trial will be grouped into 'use' and 'no use', see Appendix C: Steroids and anti-inflammatory drugs for a definition.
- number of vaccinations

For all categorical variables, the largest subgroup will be used as reference for the model estimation.

Subgroup effect will be analysed using a Cox proportional hazards regression model including treatment, subgroup and the interaction between treatment and subgroup. Vaccine efficacy will be calculated as 1 minus the hazard ratio for H56:IC31 versus placebo and presented together with the associated 95% profile confidence limits. A p-value for the joint test of interaction between treatment and subgroup will be presented, this test should be taken with caution due to few expected events and low power. Similar models will be applied for all the categorical variables. The estimated vaccine

efficacy with 95% profile confidence limits will be presented in a forest plot overall and by the above categories.

Time to TB disease recurrence will be presented by treatment and category in cumulative plots, i.e., 1 minus the KM estimates. There will be one plot for each of the above variables.

The Covid-19 pandemic will potentially have an effect on the trial conduct and on the participants. Participants will be divided into those with a relevant Covid-19 related major protocol deviation and those without, and the impact of the Covid-19 lock-down on the efficacy endpoint will be explored using an analysis a Cox proportional hazards regression model including treatment, Covid-19 related major protocol deviation or not and the interaction between treatment and Covid-19 related protocol deviation or not.

A similar exploratory analysis will be made for participants having an adverse event with the preferred term 'Corona virus infection' or 'Coronavirus test positive'.

An analysis will be omitted if data is too sparse in any of the subgroups in question.

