6.1 Rules for Discontinuing Investigational Product in an Individual Participant

Administration of additional investigational product will be discontinued for an individual participant if he/she has any of the following:

1. An objective clinical or laboratory parameter change which by the investigator is assessed as severe in intensity AND is judged to be related to the investigational product.
2. AE thought to be an allergic reaction to the investigational product, including anaphylaxis or bronchospasm.
3. Any extensive rash (>40% body surface) on the thorax, abdomen, or limbs, including but not limited to urticaria, generalized petechiae, or erythema multiforme judged to be related to the investigational product.
4. Development of active TB.
5. Development of severe disease, immunodeficiency, autoimmune disease, immunosuppression or reported HIV seroconversion.
6. Receipt of investigational drug therapy or investigational vaccine (other than investigational product received as part of this study) between 1st and 2nd vaccination or any other vaccine as described in Exclusion Criteria #12.
7. Any event that in the opinion of the site PI precludes administration of any further investigational product.
8. Pregnancy.

Participants who are withdrawn from the study within 6 months after the last product administration, will be contacted at least 6 months after the last product administration for recording of SAEs and AEs of special interest.

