- Per protocol (PP) analysis set: The PP analysis set will consist of all participants who received both doses of H56:IC31 or placebo within the specified dose intervals, who entered the evaluation period for efficacy 14 days after receipt of the 2nd dose of H56:IC31 or placebo with no HIV seroconversion, and who had no major protocol deviation of clinical or statistical significance. Major protocol deviations are defined in Section 3.1. Participants will be evaluated according to vaccination actually received.
- ITT analysis set: The ITT analysis set will consist of all randomised participants. Participants will be evaluated as randomised.
- Immunogenicity analysis set: The immunogenicity analysis set will consist of participants from the mITT population who received both doses of H56:IC31 or placebo and who are included in the immunogenicity cohort. Participants will be evaluated as randomised.

Clarifications to the protocol definitions are below in *italic*:

- *Participants with a recurrence of TB exactly on day 14 after 2nd dose are excluded from the mITT and PP analysis set.*
- *Participants who only received 1st vaccination will be excluded from the mITT if they experience a TB recurrence before Visit 6 when the visit is in the visit window, i.e., on day 67-73, or else before day 70.*
- *Efficacy endpoints are presented in section 6 and safety endpoints in section 7*

The classification of the participants will be performed before database lock (DBL).

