3.1 Major protocol deviations

Deviations from the protocol will be registered as protocol deviations with classification:

- Major
- Minor

and category

- Informed consent
- Eligibility criteria

- Withdrawal criteria not adhered to
- Dosing deviation
- Visit window
- Missed procedure(s)
- Specimen deviation
- Unblinding
- Safety reporting
- Other

Before DBL and unblinding, all protocol deviations will be evaluated. Protocol deviations classified as major can lead to exclusion from PP analysis set. The decisions will be documented in the DBL minutes.

The following will be assessed as major protocol deviations:

- Violation of inclusion criteria 5, 6 or 7
- Receipt of any investigational TB vaccine previously (excl. crit. 10)
- Receipt of any new investigational drug or investigational vaccine from Visit 1 through Visit 8 (excl. crit. 11)
- Receipt of any licensed vaccine from Visit 1 through Visit 6 (excl. crit. 12) except for SARS-Cov-2 vaccines recommended by national vaccination programs, which will be allowed if given > 28 days before and from the time of administration of clinical trial product.
- Receipt of treatment likely to modify the immune response (e.g., blood products, immunoglobulins, immunosuppressive treatment) within 42 days before Visit 3 through Visit 6. Inhaled and topical corticosteroids are permitted (excl. crit. 13)
- Received TB treatment (Rifampicin, Isoniazid, Pyrazinamide or Ethambutol) for current episode for more than 28 weeks
- Received the second vaccine outside visit window. The window was extended to two months after day 56 during the Covid-19 pandemic.
- Did not receive the 2nd vaccination
- Did not receive treatment as randomised
- HIV+ detection between Visit 3, Day 0 and Visit 6, Day 70 (14 days after the 2nd vaccination)
- Other protocol deviations which are assessed as having a clinically or statistically significant effect

Protocol deviations leading to exclusion from the PP analysis set will be summarised by treatment and in total. Number and percentages of participants will be presented, and percentages will be based on all randomised participants. Covid-19 related protocol deviations will be summarised by treatment, classification, (major/minor), and category. A similar summary of all protocol deviations will be made. Protocol deviations are rated into major or minor in the eCRF.

All protocol deviations will be listed by participant.

4 Planned Statistical Methods

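### SAP 6.2.1 fits its vaccine-efficacy-by-subgroup model to two groupings fixed after randomisation, drug use during the trial and number of vaccinations: a minor point with a cheap remedy

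*SAP*

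**What the plan says.** SAP 6.2.1 names nine baseline covariates. A separate list then adds drug use, where "use of steroids and anti-inflammatory drugs during trial will be grouped into" 'use' and 'no use', and "number of vaccinations". The analysis text makes no further distinction: "Similar models will be applied for all the categorical variables", and for the cumulative plots "There will be one plot for each of the above variables". Shells 14.2.1.26 (drug use) and 14.2.1.27 (number of vaccinations) copy shell 14.2.1.17, which prints VE with 95% limits per stratum and a joint interaction test.

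Four other places bear on how the groups form:

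- **Drugs counted.** SAP Appendix C includes NSAID classes and salicylates as well as steroids.
- **When drugs are recorded.** Under Protocol 3.6.3.5 and Table 3-3, concomitant medication is collected routinely for 14 days after each dose. After that it is collected when linked to an AE, SAE or AE of special interest.
- **Who receives dose 2.** Protocol 6.1 stops dosing for, among other reasons, a change "assessed as severe in intensity AND is judged to be related to the investigational product", and for "Development of severe disease, immunodeficiency, autoimmune disease, immunosuppression or reported HIV seroconversion".
- **Who is analysed.** SAP section 3 says "Participants who only received 1st vaccination will be excluded from the mITT if they experience a TB recurrence before Visit 6", so other one-dose participants stay in the mITT set. SAP Table 1 then removes from the time-to-event analysis anyone withdrawn before the start-timepoint.

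**The concern.** A subgroup VE can be read as effect modification because randomisation balances the arms within each baseline stratum. That protection is lost when the stratum is defined by something that happens after randomisation and may respond to the vaccine. If the vaccine prompts some participants to take an NSAID for myalgia or a sore arm, users on vaccine are a different mix of people from users on placebo. The two groups can then differ in TB risk with no true interaction.

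The two variables are not equally exposed. Drug use can begin after the mITT clock has started, may be prompted by vaccine reactions, and is recorded most completely in the reaction windows, with event-linked and ongoing use added. Number of vaccinations is normally known before the clock starts, so it carries selection but little of the timing problem.

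The SAP warns about few events and low power and drops an analysis when data are too sparse. Neither addresses this problem, because more events would not restore the randomised comparison. What is at stake is how two exploratory tables and their forest-plot rows are read.

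**Working it through.** **1. The plan's own event count.** Inputs from SAP 2.2.1: 450 per arm, 10% drop-out, 4% per year on placebo, VE 60%. Expected events: 450 × 0.9 × (0.04 + 0.016) = 22.68, which rounds to the stated 23. Required events by Schoenfeld at two-sided 20% and 80% power: 4 × (1.282 + 0.842)² / (ln 0.4)² = 21.5, so 22. The design figure reproduces.

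For the strata I use Days 70 to 421, which is 352 days or 0.964 years. Placebo: 405 × 0.04 × 0.964 = 15.6. Vaccine: 15.6 × 0.4 = 6.2. Total 21.9.

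**2. Drug use.** All rates here are assumptions. Reaction-driven use is 5% on placebo and r = 5, 15 or 30% on vaccine. Use for other reasons is 10% in both arms and carries TB risk ratio RR = 1, 1.5 or 2. True VE is the same for everyone.

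Mean relative risk among users: m = (r + 0.10 × RR)/(r + 0.10). Apparent VE among users: 1 − HR × m(vaccine)/m(placebo).

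| r on vaccine | RR | m vaccine | m placebo | ratio | VE if true 60% | VE if true 0% |
|---|---|---|---|---|---|---|
| 5% | 2 | 1.667 | 1.667 | 1.000 | 60.0% | 0.0% |
| 15% | 1.5 | 1.200 | 1.333 | 0.900 | 64.0% | 10.0% |
| 15% | 2 | 1.400 | 1.667 | 0.840 | 66.4% | 16.0% |
| 30% | 1.5 | 1.125 | 1.333 | 0.844 | 66.3% | 15.6% |
| 30% | 2 | 1.250 | 1.667 | 0.750 | 70.0% | 25.0% |

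With RR = 1, or equal r in both arms, the ratio is 1 and nothing is distorted.

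**3. Precision and the interaction test, worst row of the table.** Placebo is scaled to average 4%, so the base rate is 0.04/(0.9 + 0.1 × 2) = 0.0364.

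- User events on placebo: 405 × 0.964 × 0.0364 × 0.25 = 3.55. On vaccine: 405 × 0.964 × 0.0364 × 0.4 × 0.50 = 2.84. Total 6.4.
- SE of log HR: √(1/3.55 + 1/2.84) = 0.80, giving VE limits of −43 to 94%. At the other end of the grid (r = 5%, RR = 1), users supply 3.3 events and the limits are −339 to 96%.
- Non-user events: 12.06 and 3.41. SE of the interaction: √(1/3.55 + 1/2.84 + 1/12.06 + 1/3.41) = 1.005. Shift: ln 0.75/1.005 = −0.286. P(p < 0.05, two-sided) = 5.9% instead of 5.0%. With no vaccine effect the SE is 0.789, the shift −0.364 and the probability 6.5%.

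**4. A harsher set.** Assume 25% of participants are frail with 2 to 4 times the TB hazard, use is 30% in frail and 5% in other participants, and the vaccine prompts use in a further 10 to 30% of non-users. Apparent VE among users is then 65 to 73% at a true 60%, and 12 to 33% under no effect. In its worst cell (ratio 0.67) the expected events are 3.0 and 2.7 in users and 12.6 and 3.5 in non-users. The interaction SE is 1.03 and the false-positive rate about 7%. Under no effect (6.8 and 8.8 events on vaccine, SE 0.82) it is about 8%.

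**5. Use that starts after the clock.** In a simulation with no drug effect, counting ever-use over follow-up made the placebo use-to-no-use rate ratio 0.35 to 0.46 from timing alone. It reached 2.85 when 20% of cases took a listed drug before diagnosis. VE itself moved little: 56 to 61% against 60%.

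**6. Number of vaccinations.** Assume o = 2, 5 or 10% in both arms miss dose 2 for other reasons (RR 1 to 2), and 0, 1 or 2% more miss it on vaccine because of reactions. Ratio = [(r + o × RR)/(r + o)]/RR. The extreme case (o = 2%, r = 2%, RR = 2) gives 0.75, so VE 70% at a true 60% and 25% under no effect, on 0.98 expected events. Across the grid at VE 60%, the one-dose stratum has 0.4 to 4.1 expected events, and at least one arm has none with probability 33 to 97%.

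**The case against.** The strongest reply is that this hardly matters. The tables are exploratory, the SAP already asks for caution with the interaction test, and the shifts in steps 2 and 3 lie far inside the confidence limits. The arm difference in drug use is assumed. Protocol 1.4 describes reactions to H56:IC31 as mild to moderate, and Protocol 1.5 reports AE profiles similar to placebo for the related H4:IC31. The one-dose table will probably fall to the sparsity rule. All of this stands, and it makes the point minor. It does not make the stratum comparison a randomised one.

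A reader might infer more than the documents support:

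- *The SAP passes these variables off as baseline.* It does not; they stand in a separate list. The fault is the shared analysis without a caveat.
- *The two variables are equally at fault.* Dose count is normally fixed before the clock starts, and SAP Table 1 excludes participants withdrawn before that point.
- *The Covid models in the same section must go too.* They are also post-randomisation groupings, but the SAP states their purpose, shell 14.2.1.29 has a minimum of five subjects with an event, and no size of distortion has been worked out. A footnote is enough.
- *The per-protocol analysis can replace the dose-count analysis.* The per-protocol set is itself selected after randomisation; "Did not receive the 2nd vaccination" is one of its exclusion grounds.

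**Conclusion.** The point holds as a minor one. SAP 6.2.1 prints stratum VE and an interaction p-value for two post-randomisation groupings beside baseline subgroups, and nothing tells the reader that these are not randomised comparisons. Drug use is the real case; number of vaccinations is a weak one.

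In the main illustration user VE is overstated by at most 10 points at a true 60% and 25 points under no effect, and false positives for interaction are about 6% rather than 5%. The harsher assumptions of step 4 raise these figures somewhat without changing the conclusion. All sizes rest on assumed rates, because the documents give no drug use or missed doses by arm. The distortion vanishes if either the arm difference or the risk difference is absent.

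A reader might infer that the trial's efficacy conclusion is at risk. The documents do not support that: the primary stratified log-rank test on the mITT set uses neither variable.

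**What to change.** - Limit the VE and interaction models, the forest plot and the cumulative plots in SAP 6.2.1 to the listed baseline covariates.
- Report drug use descriptively by arm in shells 14.2.4.10 and 14.2.4.23, and number of vaccinations in 14.2.1.12, 14.2.4.11 and 14.2.4.24. All are already planned. They still show counts by arm within strata, so each needs the footnote: *post-randomisation grouping, not a randomised comparison*.
- If 14.2.1.26 or 14.2.1.27 is kept, give it the same footnote, and count drug use only up to the start-timepoint.
- Put the footnote on the Covid tables 14.2.1.28 and 14.2.1.29; no deletion is needed.
- Remove J04AA from Appendix C. Appendix E defines it as new TB treatment, so treatment of a recurrence could otherwise count as 'use'.

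The cost is SAP wording, footnotes and one ATC code, with no new output. At most two exploratory VE tables are lost, with their forest-plot rows and cumulative plots. Neither variable is among the example covariates in Protocol 7.3.1 (site, BMI, age, smoking).

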6.3 Analysis and Presentation of the Secondary Efficacy Endpoints

The secondary efficacy endpoints are:

- Rate of TB disease relapse
- Rate of TB disease reinfection

The relatedness of strains will be analysed by whole genome sequencing (WGS) using two different methods providing the single nucleotide polymorphism (SNP) distance (according to whole genome SNP analysis) and the Allele distance (according to core genome multi locus sequence typing (MLST) analysis) and the results will be categorised as follows:

The below thresholds will apply for the paired genetic variation between the Mtb isolates sampled at the screening visit and the recurrence visit:

- A distance of ≤ 5 SNPs or alleles will define a recent transmission chain, i.e. the same strain (likely relapse)
- A distance between > 5 and ≤ 12 SNPs or alleles will define strains that are genetically related (interpretation case by case are required)
- With a distance above 12 SNPs or alleles the two strains are not closely related (reinfection)

Inconsistency between SNP and allele distance will be evaluated case by case before DBL.

The SNP and allele distances will be summarised by recurrence and overall, including mean (SD), median, quartiles and minimum and maximum values. SNP and allele will be categorized using the above thresholds and summarised. TB strain information including WGS distance and tNGS lineage will be presented in listings.

Tb recurrence will be summarised by the subgroups mentioned in section 6.2.1 and type of recurrence (TB relapse, TB reinfection or undetermined).

6.3.1 Rate of TB disease relapse

TB disease relapse is defined as participants meeting the primary endpoint of TB disease recurrence AND determined by WGS of the *Mtb* isolate to be the same strain of *Mtb* as in the participant's original isolate from the time of diagnosis.

The analysis set for Rate of TB disease relapse will be the mITT set and the analysis will be repeated using the ITT analysis set (defined in section 3).

If TB disease relapse is not confirmed between start-timepoint and Day 421 (end-of-trial), the endpoint will be censored as described in Table 2.

Time to TB disease relapse will be estimated using the KM method and presented by treatment in a cumulative plot (inverted KM estimates) with 95% confidence bands, median time to TB, and the p-value from a two-sided log-rank test.

The endpoint will additionally be analysed using a Cox proportional hazard regression model, including treatment and site as categorical effects. Treatment group inference will be evaluated using a two-sided likelihood ratio test. Vaccine efficacy (VE) will be calculated as 1 minus the hazard ratio for H56:IC31 versus placebo and presented together with both 80% and 95% profile confidence limits.

The incidence of TB disease relapse per 100 person-years of follow-up and associated 95% confidence limits will be presented by treatment and trial site. The relative risk between H56:IC31 and placebo with 95% confidence limits will be presented as well.

6.3.2 Rate of TB disease reinfection

TB disease reinfection is defined as participants meeting the primary endpoint of TB disease recurrence AND determined by WGS of the *Mtb* isolate to be a different strain than in the participant's original isolate from the time of diagnosis.

The analysis set for Rate of TB disease reinfection will be the mITT set, and the analyses will be repeated for the ITT analysis set (defined in section 3).

If TB disease reinfection is not confirmed within the start-timepoint and Day 421 (end-of-trial), the endpoint will be censored as described in Table 2.

The number (and percentage) of participants meeting this secondary endpoint will be summarised by treatment group.

Time to TB disease reinfection will be estimated using the KM method and presented by treatment in a cumulative plot (inverted KM estimates) with 95% confidence bands, median time to TB, and the p-value from a two-sided log-rank test.

The endpoints will additionally be analysed using a Cox proportional hazard regression model, including treatment and site as categorical effects. Treatment group inference will be evaluated using

a two-sided likelihood ratio test. Vaccine efficacy (VE) will be calculated as 1 minus the hazard ratio for H56:IC31 versus placebo and presented together with both 80% and 95% profile confidence limits.

The incidence of TB disease reinfection per 100 person-years of follow-up and associated 95% confidence limits will be presented by treatment. The relative risk between H56:IC31 and placebo with 95% confidence limits will be presented as well.

6.4 Analysis and presentation of the secondary immunogenicity endpoints

The secondary immunogenicity endpoints are:

- Antigen specific cell mediated immune responses by WB ICS
- Humoral immune responses by IgG ELISA

The immunogenicity analysis set will be used for these endpoints, and the immunogenicity cohort will be used for an exploratory analysis.

6.4.1 Antigen specific cell mediated immune responses by WB ICS

Antigen specific cell mediated immune responses by WB ICS at baseline (Visit 3, Day 0), and 14 days after the 2nd vaccination (Visit 6, Day 70) is a secondary endpoint and the primary immunogenicity endpoint. For assessment of the immunogenicity of H56:IC31 by WB ICS, only whole blood samples from the immunogenicity cohort are included (See sections 1 and 2.2).

Responses will be measured by flow cytometry (up to 15 parameters) with the WB ICS assay. The variables of interest for assessment of antigen-specific cell-mediated immune response to vaccination will be the percentage of CD4⁺ and CD8⁺ T-cells that express the cytokines IL-2, IFN- γ , TNF- α , and IL-17 in the following combinations:

- H56 protein-specific CD4⁺ T-cells expressing the total cytokine response, i.e., any combination of IL-2, IFN- γ , TNF- α , and/or IL-17
- H56 protein-specific CD4⁺ T-cells co-expressing IL-2 and TNF- α
- H56 protein-specific CD4⁺ T-cells co-expressing IL-2, IFN- γ , and TNF- α
- H56 protein-specific CD8⁺ T-cells expressing any combination of IL-2, IFN-g, TNF- α , and/or IL-17 (total response)

The percentages of T-cell responses will be presented in summary tables and box plots including median, quartiles and range by treatment and visit including change from Visit 3 to Visit 6.

The immunogenicity analysis set will also be used for analysis of antigen specific cell mediated immune responses by WB ICS, please see Appendix A.

